8.3 Primary Efficacy Endpoint and Analyses

8.3.1 Primary Efficacy Endpoint

The primary endpoint for the primary analysis of efficacy is:

- Proportion of subjects achieving at least a 75% reduction in Eczema Area and Severity Index from Baseline (EASI 75) at Week 16;

Hypotheses corresponding to the primary objective and endpoint is:

- The proportion of subjects with EASI 75 treated with upadacitinib for Atopic Dermatitis is greater than that of dupilumab at Week 16.

8.3.2 Handling of Missing Data for the Primary Efficacy Endpoint

The NRI-C will be the primary approach for missing data handling in the analyses of the primary efficacy endpoint. The NRI-NC and MI approaches will be used as sensitivity analyses.

8.3.3 Primary Efficacy Analysis

For ITT Population, comparisons between each upadacitinib group and the dupilumab group will be conducted using the CMH test, adjusting for vIGA-AD categories. NRI-C will be the primary approach to handle missing values. The NRI-NC and MI approaches will be used as sensitivity analyses.

8.3.4 Additional Analyses of the Primary Efficacy Endpoint

The primary efficacy analysis will be performed on PP Population as a sensitivity analysis of the primary endpoint. The definition of PP Population can be found in Section 4.0. The per-protocol analysis will be based on the NRI-C approach.

8.4 Secondary Efficacy Analyses

8.4.1 Key Secondary Efficacy Analyses

The secondary endpoints for the primary analysis of efficacy are:

- Percent change in Worst Pruritus NRS from baseline to Week 16

- Proportion of subjects achieving at least a 100% reduction in Eczema Area and Severity Index from Baseline (EASI 100) at Week 16;
- Proportion of subjects achieving at least a 90% reduction in Eczema Area and Severity Index from Baseline (EASI 90) at Week 16;
- Percent change in Worst Pruritus NRS from Baseline to Week 4;
- Proportion of subjects achieving a 75% reduction in EASI (EASI 75) from Baseline at Week 2;
- Percent change in Worst Pruritus NRS from Baseline to Week 1
- Proportion of subjects achieving an improvement (reduction) in Worst Pruritus NRS ≥ 4 from Baseline at Week 16

Hypotheses corresponding to the endpoints are:

- The percent change in Worst Pruritus NRS from baseline in subjects treated with upadacitinib for Atopic Dermatitis is greater than that of dupilumab at Week 16.
- The proportion of subjects with EASI 100 treated with upadacitinib for Atopic Dermatitis is greater than that of dupilumab at Week 16.
- The proportion of subjects with EASI 90 treated with upadacitinib for Atopic Dermatitis is greater than that of dupilumab at Week 16.
- The percent change in Worst Pruritus NRS from baseline in subjects treated with upadacitinib for Atopic Dermatitis is greater than that of dupilumab at Week 4.
- The proportion of subjects with EASI 75 treated with upadacitinib for Atopic Dermatitis is greater than that of dupilumab at Week 2.
- The percent change in Worst Pruritus NRS from baseline in subjects treated with upadacitinib for Atopic Dermatitis is greater than that of dupilumab at Week 1.
- The proportion of subjects with an improvement (reduction) in Worst Pruritus NRS ≥ 4 with upadacitinib for Atopic Dermatitis is greater than that of dupilumab at Week 16.

Secondary efficacy endpoints will be analyzed by comparing upadacitinib treatment group and dupilumab. The categorical endpoints and continuous endpoint will be analyzed by CMH and MMRM, respectively, and the corresponding analyses are specified in Section 8.1.

Worst Pruritus NRS will be analyzed based on weekly rolling averages of daily scores.

8.4.2 Supportive Secondary Efficacy Analyses

The NRI-C will be the primary approach for missing data handling in the analyses of the binary secondary efficacy endpoints. The NRI-NC approach will be used as sensitivity analyses. MMRM will be the primary and the only approach for continuous endpoint.

8.5 Additional Efficacy Analyses

For ITT Population, additional efficacy endpoints will be compared between the upadacitinib and dupilumab treatment groups. The categorical endpoints will be analyzed by CMH, and the corresponding analyses are specified in Section 8.1.

8.6 Efficacy Subgroup Analyses

To evaluate the consistency of the efficacy over demographic and other Baseline characteristics, the primary endpoint will be analyzed in the following subgroups.

- Age Group (< 40 years, \geq 40 – < 65 years, \geq 65 years)
- Sex (male, female)
- BMI (normal: < 25, overweight: \geq 25 – < 30, obese: \geq 30)
- Race (White, Asian, Black, and Other)
- Weight (< median, \geq median)
- Geographic regions (US/PR/Canada, Other)
- Baseline vIGA-AD (moderate or milder [vIGA-AD \leq 3], severe [vIGA-AD 4])
- Baseline EASI (< median, \geq median)
- hsCRP (< median, \geq median)
- Previous systemic therapy (with and without)

Any RACE subgroups with fewer than 10% subjects will be combined with Other for analyses. Age \geq 65 years or BMI \geq 30 subgroups will be combined with their adjacent subgroup when having fewer than 10% subjects. For any subgroup, if there are zero subjects within a stratum in any treatment group, the CMH model will not be adjusted by the stratification factors.

9.0 Safety Analyses

9.1 General Considerations

Safety data will be summarized for the Safety Population. Safety summaries will be presented by treatment group and total. For the safety analysis, subjects are assigned to a treatment group based on the treatment actually received, regardless of the treatment randomized.

A subject's actual treatment will be determined by the most frequent dose regimen received.

Safety analyses will include adverse events, laboratory, and vital sign measurements. Missing safety data will not be imputed.

9.2 Adverse Events

9.2.1 Treatment-Emergent Adverse Events

Treatment-emergent adverse events (TEAEs) are defined as any adverse events that begin or worsen in severity after initiation of upadacitinib/dupilumab through 30 days following the last dose of upadacitinib or 84 days following the last dose of dupilumab, regardless of any study drug interruption. If a missing or an incomplete onset date is collected for an adverse event, the event will be assumed to be treatment-emergent unless there is other evidence that confirms that the event is not treatment-emergent (e.g., the event end date is prior to the study drug start date).

Pre-treatment AEs are defined as AEs that occurred before the first dose of upadacitinib/dupilumab. Post-treatment AEs are defined as AEs that occurred beyond 30 days after the last dose of upadacitinib or 84 days after the last dose of dupilumab.

Adverse event data will be coded using the Medical Dictionary for Drug Regulatory Activities (MedDRA) version 22.1 or most up to date version.

Summary tables will be presented as follows:

1. Adverse Event Overview

An overview of AEs will be presented consisting of the number and percentage of subjects experiencing at least one event for each of the following AE categories 1) from Baseline to Week 16 visit and 2) the entire treatment period, respectively:

- Any treatment-emergent AE
- Any treatment-emergent AE related to study drug according to the investigator
- Any severe treatment-emergent AE (Grade 3 and above according to NCI CTCAE version 5.0)
- Any serious treatment-emergent AE (SAE)
- Any treatment-emergent AE leading to discontinuation of study drug
- Any treatment-emergent AE leading to death
- AEs of Special Interest
- Other Safety Topics of Interest
- Any treatment-emergent SAE related to study drug according to the investigator
- Any TEAE leading to death
- All deaths
 - Deaths occurring \leq 30 days after last dose of upadacitinib or \leq 84 days after last dose of dupilumab
 - Deaths occurring $>$ 30 days after last dose of upadacitinib and $>$ 84 days after last dose of dupilumab

2. Treatment-Emergent Adverse Events by System Organ Class and Preferred Term

TEAEs will be summarized and presented using primary MedDRA version 22.1 or later by system organ class (SOC) and preferred terms (PT) 1) from Baseline to Week 16 visit and 2) the entire treatment period, respectively. The SOCs will be presented in alphabetical order, and the PTs will be presented in alphabetical order within each SOC. Subjects reporting more than one adverse event for a given MedDRA preferred term will be counted only once for that term (most severe incident for the severity tables and most related incident for the relationship tables). A subject who reports more than 1 AE in different SOCs will be counted only once in the overall total. Subjects reporting more than one type of adverse event will be counted only once in the overall total.

The following summaries of adverse events will be generated:

- All TEAEs
- Treatment-emergent serious adverse events
- Treatment-emergent severe adverse events
- TEAEs related to study drug according to the investigator
- TEAEs leading to discontinuation of study drug
- TEAE leading to death

3. Treatment-Emergent Adverse Events by Maximum Toxicity

The severity grading of AEs follows the NCI CTCAE version 5.0.

TEAEs will be summarized by maximum toxicity. For summaries of AEs by toxicity, each subject is counted only once – according to the maximum toxicity level observed. If a subject has an AE with an unknown toxicity, then the subject will be counted in the toxicity category of "unknown." The only exception is that if the subject has another occurrence of the same AE with the most extreme, non-fatal NCI CTCAE toxicity (i.e., grade 4) or is fatal (grade 5). In this case, the subject will be counted under grade 4 if

non-fatal or 5 if fatal. For tables that look at severity instead of toxicity, the subjects that have an unknown NCI CTCAE grade but another occurrence of the same AE that is considered severe (grade ≥ 3) will be counted under severe.

4. Treatment-Emergent Adverse Events by Preferred Term in Decreasing Frequency

TEAEs occurring in either treatment groups will be summarized by MedDRA PT in decreasing frequency of upadacitinib, respectively.

5. Overview of Adverse Events by 100 Patient Years

AEs occurring during the entire study will be presented by event rate per 100 patient years. These will be presented by treatment group for the following AE categories 1) from Baseline to Week 16 visit and 2) the entire treatment period, respectively.

- Any TEAE
- Any treatment-emergent SAE
- Any TEAE leading to discontinuations of study drug
- Any severe TEAE
- Any TEAE related to study drug according to the investigator
- Any treatment-emergent SAE related to study drug according to the investigator
- Any TEAE leading to death
- TEAEs of Special Interest
- Other Safety Topics of Interest

Additional AEs may be considered for tabulation/summary based on recommendations from Clinical and Safety as deemed appropriate.

AEs per 100 patient-years of exposure is defined as the number of AEs divided by the total exposure in 100 patient-years. Note that one event per preferred term per day per subject will be counted in the calculation of the number of AEs (i.e., a preferred term will

not be counted twice on the same day for the same subject). See the calculation method below:

$$100 * (\text{Number of TEAEs}) / (\text{Total Patient Years})$$

where total patient years is defined as the sum of the study drug duration (defined in Section 6.0) of all subjects normalized by 365.25, and rounded to 1 decimal place.

6. Treatment-Emergent Adverse Events Rates per 100 Patient-Years of Study Drug Exposure by SOC and PT

For each treatment group, the TEAE rate per 100 patient-years of exposure will be calculated overall, for each SOC and each PT, for each of the following events:

- All TEAEs
- Treatment-emergent serious adverse events
- Treatment-emergent severe adverse events
- TEAEs related to study drug according to the investigator
- TEAEs leading to discontinuation of study drug
- TEAE leading to death

7. Listing of Adverse Events

The following additional summaries will be provided for treatment-emergent adverse events, unless otherwise specified.

- List of subject numbers associated with each PT for TEAEs.
- List of subject numbers associated with each PT for -TEAEs related to study drug according to the investigator Listing of pretreatment AEs.
- Listing of treatment-emergent SAEs.
- Listing of TEAEs leading to discontinuation of study drug.
- Listing of all deaths.
- Listing of treatment-emergent AESIs.

- Listings of other safety topics of interest
- Listings of pre-treatment AEs.

8. Acne Adverse Events

The investigator-identified acne AEs will be summarized by involvement, morphology, and acne risk factors.

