2.2 Study Design Overview

This is a Phase 3b, randomized, double-blind, double-dummy, active comparator-controlled multicenter study that will evaluate the safety and efficacy of upadacitinib versus dupilumab in adults (≥ 18 to ≤ 75 years of age) with moderate to severe AD who

[figure not shown]
are candidates for systemic therapy. Eligible subjects must have a documented history of inadequate response to treatment with topical AD treatments or documented use of systemic treatment for AD within 6 months prior to the Baseline Visit or for whom topical treatments are otherwise medically inadvisable.

The study is comprised of a 35-day Screening Period, a 24-week double-blind treatment period, and an End-of-Treatment Follow-up Visit. The End-of-Treatment Follow-up Visit will be 12 weeks after the last injection. Subjects who meet eligibility criteria will be randomized in a 1:1 ratio to one of the two arms as shown below:

- Treatment A (N = 325): Daily oral doses of upadacitinib 30 mg from the Baseline visit until the Week 24 visit, and placebo pre-filled syringe administered at the baseline visit (2 subcutaneous [SC] injections), followed by placebo pre-filled syringe (1 injection) every other week until the Week 22 visit.
- Treatment B (N = 325): Dupilumab 600 mg (2 × 300 mg dupilumab SC injection) administered at the Baseline visit, followed by dupilumab 300 mg SC injection every other week until the Week 22 visit and daily oral doses of placebo tablets from the Baseline visit until the Week 24 visit.

Randomization will be stratified by baseline disease severity (moderate validated Investigator Global Assessment for atopic dermatitis [vIGA-AD 3] vs. severe [vIGA-AD 4]) and age (< 40, ≥ 40 to < 65, ≥ 65 years). The subject's age at baseline will be used for randomization and throughout the duration of the study.

The schematic of the study is shown in [Figure 1](#).

Figure 1. **Study Schematic**

BL = Baseline; SC = subcutaneous

* Dupilumab 300 mg SC injection will be administered every other week starting at the Week 2 visit and until the Week 22 visit, after an initial dose of 600 mg at the Baseline visit.

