6.0 Study Drug Duration and Compliance

Study Drug Duration (in Days):

Summary of study drug duration and study drug compliance will be provided for each treatment group for the Safety Population 1) from Baseline to Week 16 visit and 2) the entire treatment period, respectively. Study drug duration (days) will be summarized using the number of subjects, mean, standard deviation, minimum, median and maximum for each treatment group.

1. From Baseline to Week 16:

- Duration of upadacitinib is defined for each subject as
 - The minimum (last dose date of upadacitinib, Week 16 visit date -1) minus first dose date of upadacitinib +1 if the Week 16 visit date is non-missing, and
 - The minimum (last dose date of upadacitinib, nominal Week 16 visit date-1) minus first dose date of upadacitinib +1 if the Week 16 visit date is missing. Here nominal Week 16 visit date is defined as first dose date of upadacitinib + 112.
- Duration of dupilumab is defined for each subject as the last dose date of dupilumab before Week 16) minus first dose date of dupilumab +14. The last dose of dupilumab before Week 16 is defined as the last dose date of dupilumab within 105 days (the upper bound of Week 14 dupilumab administration window) of the first dose date of dupilumab.

2. The entire treatment period:

- Duration of upadacitinib is defined for each subject as last dose date of upadacitinib minus first dose date of upadacitinib +1,
- Duration of dupilumab is defined for each subject as last dose date of dupilumab minus first dose of dupilumab date +14.

Compliance:

Treatment compliance will be summarized by treatment group in the Safety Population for 1) from Baseline to Week 16 visit and 2) the entire treatment period, respectively.

1. From Baseline to Week 16:

- Upadacitinib compliance is defined as the number of upadacitinib (or placebo for upadacitinib) actually taken prior to Week 16 (i.e., the difference between the number of tablets dispensed and the number of tablets returned) by the subject divided by the number of tablets planned to be taken by the subject during the first 16 weeks.

- Dupilumab compliance is defined as the number of dupilumab (or placebo for dupilumab) injections administered during the subject's participation prior to Week 16 by the subject divided by the number of injections planned during the subject's participation during the first 16 weeks.

2. The entire treatment period:

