9.3 Analysis of Laboratory Data

Analyses of selected laboratory data will be performed in safety population. Data collected from central and local laboratories, including additional laboratory testing due to an SAE, will be used in all analyses, except for Baseline derivation where SAE-triggered laboratory assessments on or before the first dose of study drug will be excluded.

For the analysis of laboratory data, values observed up to 30 days after the last dose of upadacitinib or 84 days after the last dose of dupilumab will be included.

All laboratory parameters to be collected in this study are listed below. Laboratory parameters will be reported using the standard international (SI) units. The selected clinical laboratory tests defined in the protocol operations manual (e.g., hematology and clinical chemistry) will be summarized.

Table 2. List of Laboratory Values

Clinical Laboratory Tests		
Hematology	Clinical Chemistry	Other Tests
Hematocrit	BUN	Central Lab Tests: Estimated glomerular filtration rate (eGFR)
Hemoglobin	Creatinine	International normalized ratio (INR)
RBC count	Total bilirubin	Serum pregnancy (beta human chorionic gonadotropin [bHCG]) test
WBC count	INR (reflex only) ^a	Hepatitis Screening:
Neutrophils	Albumin	Hepatitis B surface antigen (HBs Ag)
Bands	ALT	Hepatitis B surface antibody (HBs Ab)
Lymphocytes	AST	Hepatitis B core antibody (HBc Ab)
Monocytes	Alkaline phosphatase	Hepatitis B virus deoxyribonucleic acid polymerase chain reaction (HBV DNA PCR [rIreflex only])
Basophils	CPK	Hepatitis C virus antibody (HCV Ab)
Eosinophils	Sodium	Hepatitis C virus ribonucleic acid (HCV RNA [reflex only])
Platelet count	Potassium	Human immunodeficiency virus antibody (HIV Ab)
Urinalysis		
Specific gravity	Bicarbonate/CO ₂	QuantiFERON-TB Gold
Ketones	Chloride	High-sensitivity C-reactive protein (hsCRP)
pH	Calcium	Follicle stimulating hormone (FSH) ^b
Protein	Inorganic phosphorus	Drug and alcohol screen
Blood Glucose	Uric acid	Local Lab Tests:
Urobilinogen	Total protein	Urine pregnancy test
Bilirubin	Glucose	Varicella antibody, if indicated
Leukocytes	Cholesterol	PPD test / T-SPOT TB
Nitrites	LDL-C	
Microscopic examination, if needed	HDL-C	
	Triglycerides	

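### Entire-period AE rates count events to 30 or 84 days after the last dose but divide by time on drug only, which can favour upadacitinib.

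*SAP*

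**What the plan says.** **Numerator.** SAP 9.2.1 defines treatment-emergent events as those that begin or worsen after first dose "through 30 days following the last dose of upadacitinib or 84 days following the last dose of dupilumab". Events are called post-treatment only beyond those limits, so an event in the tail is a TEAE. Protocol 7.4 uses the same windows.

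**Denominator.** SAP 9.2.1 item 5 sets the rate at 100 times the number of TEAEs over total patient-years, "where total patient years is defined as the sum of the study drug duration (defined in Section 6.0"). For the entire treatment period SAP 6.0 says "Duration of upadacitinib is defined for each subject as last dose date of upadacitinib minus first dose date of upadacitinib +1" and "Duration of dupilumab is defined for each subject as last dose date of dupilumab minus first dose of dupilumab date +14". Neither duration contains the post-dose window.

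**Period.** Item 5 opens with "AEs occurring during the entire study will be presented by event rate per 100 patient years" and then names two periods, Baseline to Week 16 and the entire treatment period. Item 6, the rates by SOC and PT, names no period at all.

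**Follow-up and roll-over.** Under Protocol 6.1, AEs are collected to 12 weeks after the last injection in both arms. Under Protocol 4.1, every completer may enter an open-label upadacitinib study, and the 12-week follow-up visit is for those who do not. The SAP does not say whether TEAE counting stops at the first open-label dose.

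**The concern.** A rate per patient-year needs events and time from the same interval. Here the events run past the end of the counted time, and by a different amount in each arm. The reported rate is inflated in both arms, and more in the dupilumab arm because its window is longer. Two drugs with identical risk can then show a ratio below 1 for upadacitinib from the calculation alone.

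The study objective covers safety as well as efficacy against dupilumab. Protocol 7.4 promises events per 100 patient-years for SAEs, deaths, AEs leading to discontinuation and AEs of special interest. These tables are what a reader will use to compare the arms after allowing for exposure.

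**Working it through.** The documents give no AE rate or patient-year total, so there is no figure of the plan's own to reproduce. I applied the SAP definitions by day count.

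**Inputs for a completer**
- Last tablet about Day 168 (SAP 2.2: daily until the Week 24 visit).
- Last injection at Week 22, Day 155 (SAP 2.2).
- Patients per arm: 325 (SAP 2.4).

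**Denominators (SAP 6.0)**
- Upadacitinib: 168 − 1 + 1 = 168 days.
- Dupilumab: 155 − 1 + 14 = 168 days.
- Per arm: 325 × 168 / 365.25 = 149.5 patient-years.

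**Days on which events count (SAP 9.2.1)**
- Upadacitinib: to Day 168 + 30 = 198, so 30 days are outside the denominator.
- Dupilumab: to Day 155 + 84 = 239, so 71 days are outside.

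**Completers.** Let *q* be the off-drug event rate relative to on-drug, and *r* the share who roll over, with counting stopped at roll-over. With equal true risk the reported upadacitinib/dupilumab ratio is

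(168 + 30*q*(1 − *r*)) / (168 + 71*q*(1 − *r*)).

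| Assumption | Ratio |
|---|---|
| *q* = 1, *r* = 0 | 198/239 = 0.828 |
| *q* = 1, *r* = 0.5; or *q* = 0.5, *r* = 0 | 183/203.5 = 0.899 |
| *q* = 1, *r* = 0.8 | 174/182.2 = 0.955 |
| *q* = 0.5, *r* = 0.8 | 171/175.1 = 0.977 |
| *r* = 1, or *q* = 0 | 1.00 |

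In the first row the inflation is 198/168 = 1.18 against 239/168 = 1.42. A true ratio of 239/198 = 1.21 against upadacitinib would be reported as 1.00. Counting the dupilumab gap as 70 days instead of 71 gives 198/238 = 0.832.

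**Subjects stopping at Week 8, *q* = 1.** Upadacitinib: 86 counted days over 56. Dupilumab: 127/56 if the last injection was at Week 6, or 141/70 if at Week 8. The ratios are 0.68 and 0.76. They describe the stoppers alone, not the whole arm.

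**Whole arm: 10% stop at Week 8 (last injection Week 6, no roll-over) and 80% of completers roll over**
- Both denominators: 0.9 × 168 + 0.1 × 56 = 156.8.
- *q* = 1: upadacitinib 0.9 × 174 + 0.1 × 86 = 165.2; dupilumab 0.9 × 182.2 + 0.1 × 127 = 176.68; ratio 0.935.
- *q* = 0.5: upadacitinib 0.9 × 171 + 0.1 × 71 = 161.0; dupilumab 0.9 × 175.1 + 0.1 × 91.5 = 166.74; ratio 0.966.

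**Week 16 tables, *q* = 1.** Counted days are capped at 112, so only early stoppers matter.
- 15% stopping at Week 8, last injection Week 6: (0.85 × 112 + 0.15 × 86)/112 = 108.1/112 = 0.965 (the denominators are equal and cancel).
- 5% stopping, last injection Week 8: upadacitinib 110.7/109.2 = 1.014; dupilumab 112/109.9 = 1.019; ratio 0.995.

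**Direction.** The sign reverses for completers only if *q* is more than 71/30, about 2.4 times, as high for upadacitinib as for dupilumab.

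**The case against.** The strongest reply is that the entire treatment period already means time on drug. SAP 6.0 uses that phrase for drug duration, and SAP 2.2 separates treatment from follow-up: "The study is comprised of a 35-day Screening Period, a 24-week double-blind treatment period, and an End-of-Treatment Follow-up Visit". On that reading most of the mismatch goes. The reading is possible but not written. The numerator in item 5 is the number of TEAEs, which by definition includes the tail. Item 5 is introduced as covering the entire study, and item 6 has no period wording that could limit it.

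Two other passages that point to the tail-inclusive reading carry little weight. The AE overview is given "for each of the following AE categories 1) from Baseline to Week 16 visit and 2) the entire treatment period" and has rows for deaths up to and beyond 30/84 days. That sentence also covers the Week 16 period, so those rows define neither period. SAP 9.3 states that "values observed up to 30 days after the last dose of upadacitinib or 84 days after the last dose of dupilumab will be included", and SAP 9.4 does the same for vital signs, but no rate is involved there. The conclusion does not need either.

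The reply on size largely stands. The 0.83 needs no roll-over, full follow-up and a constant event rate. Roll-over is open to every completer, and the activity schedule has one visit after Week 24, so recording in the tail is probably sparser. The comparison is descriptive, no test is planned, and percentages are tabulated alongside.

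The drug-specific windows are deliberate, based on five half-lives in Protocol 7.4, and are not an error. The fault is in dividing by time that does not match them.

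**Conclusion.** The concern holds. As written, the rate formula pairs TEAEs counted to 30 or 84 days after the last dose with a duration that leaves out about 30 of those days on upadacitinib and 71 on dupilumab. No matching rule is stated.

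With equal true risk and the same relative off-drug rate in both arms, the reported ratio is either 1.00 or tilted towards upadacitinib. It is 0.83 at the extreme and 0.94 to 0.97 for the whole arm under 10% stopping at Week 8 and 80% roll-over. The Week 16 tables move by at most a few percent. These sizes rest on assumed roll-over, stopping and off-drug rates. That the rule is missing does not depend on them.

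This does not touch the efficacy conclusions. It should be settled because the exposure-adjusted safety comparison with dupilumab is promised in the protocol and the correction is small.

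**What to change.** 1. **Main change.** In all tables per 100 patient-years, count only TEAEs with onset inside the SAP 6.0 duration used as denominator: first dose through the last upadacitinib dose date, or through 13 days after the last dupilumab dose. Use the Week 16 durations for the Week 16 rates. With equal on-drug risk this gives 1.00 whatever the off-drug rate. Keep the 30/84-day definition for the percentage tables, so that later events stay reported.
2. **Open-label entry.** State that TEAE counting stops at the first open-label dose.
3. **If drug-specific windows are kept for any rate**, divide by time at risk over the same window, and note that the result still depends on the off-drug rate. With no roll-over the ratio (168 + 30*q*)/198 ÷ (168 + 71*q*)/239 is 1.00, 1.09 or 1.21 for *q* = 1, 0.5 or 0.
4. **Optional.** Add one supportive entire-period summary with a common window of 12 weeks after the last injection in both arms, with matching time at risk, cut at last contact or first open-label dose. It adds about 41 upadacitinib days beyond that drug's own window (Day 239 against Day 198). It is neutral only if off-drug rates are alike: (168 + 71 × 0.5)/239 = 0.85 if the upadacitinib off-drug rate is half its on-drug rate and the dupilumab rate is unchanged, and 1.17 in reverse.
5. **Separate wording point.** Protocol 6.1 defines TEAEs by 12 weeks after the last injection in both arms, unlike Protocol 7.4 and SAP 9.2.1. The passages must be reconciled.

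**Cost.** The main change needs SAP wording and one derived variable, with no new data collected. The price is that SAEs and AEs of special interest starting after the drug period leave the rate tables and appear only in the percentages. Item 2 needs first-dose dates from the open-label study; SAP 5.0 lists only whether subjects enrolled in it. Item 4 adds one summary.
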